### ● Purpose of the study

- To gather baseline data on the prevalence and impact of musculoskeletal symptoms among otolaryngologists in George Washington University Hospital network.
- To examine the influence of otolaryngology stretching micro-breaks (OSMB) on their physical performance, mental focus, and self-reported pain and discomfort among otolaryngologists in George Washington University Hospital network.

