### ● Recruitment Methods

- An E-mail will be sent out to attending physicians and residents affiliated at GWU and Children's National inviting them to participate in the study.

- **Research Locations**

- George Washington University Hospital
- Children's National Medical Center

[figure not shown]
- **Methods**

- **Intervention**

- **Otolaryngology stretching micro-breaks (OSMB)**= standardized microbreak stretch that is designed to perform intraoperatively within the sterile field at medically convenient 20-40 min intervals throughout each procedure.

- **Assessment tools (see the table of content to view survey)**

[figure not shown]
- Preliminary questionnaire- given at the beginning of the study
    - Assess demographic information, ergonomic questions, and musculoskeletal symptom questions
  - Pre-surgery questionnaire (baseline)- given prior to each surgery to establish a baseline
    - Body part discomfort (validated survey with 0-5 score on the neck, shoulder R/L, hand R/L, lower/upper back, knee R/L, foot R/L)

- Post-surgery questionnaire for CONTROL day- given after each surgery
  - Surg-TLX and GOAL questionnaire- assess the degree of difficulty of the surgery
  - Body part discomfort sore
- Post-surgery questionnaire for INTERVENTION day- - given after each surgery
  - Surg-TLX and GOAL questionnaire- assess the degree of difficulty of the surgery
  - Body part discomfort sore
  - Questions on OSMB
- Exit questionnaire after the study is completed
  - 2 questions asking whether the participant would incorporate OSMB in their routine OR cases, and would recommend OSMB to colleagues.

- **Study design**

- Crossover study design
- Control: 3 Non-OSMB surgical days
- Intervention: 3 OSMB surgical days
- In order to reduce confounding variables, study will focus on open neck cases. (e.g. thyroidectomy, parathyroidectomy, neck dissection, etc)
- We will adjust for surgical duration, and use Surg-TLX, and GOAL questionnaires to show no statistically significant difference between control and intervention surgical cases.
- Outcome measures
  - Primary outcome= difference between self-reported body part discomfort score from before/after surgery
    - Control the surgical environment and difficulty using Surg-TLX and GOAL questionnaires. The score should be statistically insignificant among various surgeries.
  - Secondary outcome= impact of OSMB on physical performance, discomfort/pain, fatigue, and mental focus

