## ● Statistics

- Descriptive statistics to calculate the prevalence and impact of musculoskeletal symptoms
- Descriptive statistics to characterize demographic information on participants
- Linear mixed models: Used to test for an association between pain and the targeted micro-break intervention
- Statistical significance is set at 0.05 (Bonferroni adjustment for measurement on 11 body parts.)

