**Ergonomic Questions**

Have you experienced any work-related musculoskeletal symptoms while performing the surgery?

Yes  
 No

What is the PRIMARY area of your body that is most bothersome to you? (select one answer)

Neck  
 Shoulder  
 Lower back  
 Upper back  
 Hips  
 Legs  
 Feet  
 Arms  
 Hands  
 None

What is the SECONDARY area of your body that is most bothersome to you? (select one answer)

Neck  
 Shoulder  
 Lower back  
 Upper back  
 Hips  
 Legs  
 Feet  
 Arms  
 Hands  
 None

What is the TERTIARY area of your body that is most bothersome to you? (select one answer)

Neck  
 Shoulder  
 Lower back  
 Upper back  
 Hips  
 Legs  
 Feet  
 Arms  
 Hands  
 None

Confidential

Page 3 of 4

---

When did you begin to experience these musculoskeletal symptoms?

PGY1  
 PGY2  
 PGY3  
 PGY4  
 PGY5  
 During fellowship  
 0-1 year into practice  
 2-5 years into practice  
 6-10 years into practice  
 11 or more years into practice

---

How often do these musculoskeletal symptoms occur?

Rarely  
 Half of surgery cases  
 Most surgery cases  
 Every surgery case

---

Please estimate the timeframe of symptom onset?

< 30min  
 30min to 1hr  
 1-3hrs  
 3-6hrs  
 >6hrs  
 Post-surgery  
 Following day  
 Other

---

Other (please specify)

---

Does the use of specific surgical equipment elicit symptoms more frequently? (select all that applies)

Headlight  
 Robot  
 Endoscopic instruments  
 Loupes  
 Microscope  
 Other

---

What risk reduction strategies do you perform in the OR to help alleviate musculoskeletal issues? (select all that applies)

Ignore it  
 Adjust the surgical field  
 Change the bed height  
 Use a step stool to adjust the height  
 Change instruments  
 Stools  
 Standing pads  
 Timed-Breaks  
 Intraoperative stretching  
 Change position  
 Time away from the OR  
 Treatment  
 Other

---

Others (please specify)

---

Have you had to stop performing this type of surgery due to musculoskeletal symptoms?

Yes  
 No

---

Have you ever taken time off of work due to musculoskeletal pain/injury?

Yes  
 No

---

*Confidential*

Page 4 of 4

---

Have you ever seen any of the following for treatment or consultation? (Select all that apply)

- No treatment
- Massage therapist
- Acupuncture
- Personal trainer
- Physical therapist
- Chiropractor
- PM&R
- Physician
- Surgeon
- Other

---

Other (please specify)

---

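### The care-seeking item on the preliminary questionnaire names no musculoskeletal complaint, so unrelated care may inflate the descriptive impact percentage for the first objective

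*Protocol*

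**What the plan says.** The Protocol's Purpose of the study section gives the first aim as "To gather baseline data on the prevalence and impact of musculoskeletal symptoms among otolaryngologists" in the hospital network. The Statistics section plans "Descriptive statistics to calculate the prevalence and impact of musculoskeletal symptoms". The preliminary questionnaire, given once at the start, is the form described as serving to "Assess demographic information, ergonomic questions, and musculoskeletal symptom questions".

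On that form, under Ergonomic Questions, the prevalence item is "Have you experienced any work-related musculoskeletal symptoms while performing the surgery". Later come three items that read naturally as measures of impact:

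- Stopping surgery: "Have you had to stop performing this type of surgery due to musculoskeletal symptoms"
- Time off: "Have you ever taken time off of work due to musculoskeletal pain/injury"
- Care sought: "Have you ever seen any of the following for treatment or consultation? (Select all that apply"

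The options for the last item run from No treatment, massage therapist, acupuncture and personal trainer, through physical therapist, chiropractor and PM&R, to Physician, Surgeon and Other. The protocol does not list which items make up impact.

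**The concern.** A descriptive percentage means only what its item asks. The stop-surgery and time-off items each carry their own reference to musculoskeletal symptoms or injury, but the care-seeking item does not. Surgeons, like other adults, see physicians and surgeons for many reasons, and the item asks about any time in the past. If some answer literally, the share reported as having sought care for musculoskeletal symptoms will include care for other conditions.

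The wording is fixed on the form, so a statistical analysis plan could not repair this afterwards. If the form never asks why a provider was seen, the reason cannot be recovered.

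The time-off item raises a related but weaker question. It is tied to musculoskeletal problems but not to work, while the prevalence item is limited to work-related symptoms felt while operating. Reported side by side, the two percentages would describe different conditions.

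**Working it through.** The protocol states no figure for care-seeking or time off, so there is nothing to reproduce. The check sets the item wordings side by side and then works out what one misread answer is worth.

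**Wording of the items**

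| Item | Names a musculoskeletal problem? | Limited to work? | Period |
|---|---|---|---|
| Opening symptom item | Yes | Yes, while operating | None stated |
| Onset and frequency | Yes, by referring back | Only through the opening item | Not applicable |
| Stop-surgery | Yes | Not stated | None stated |
| Time off | Yes, pain or injury | No | Ever |
| Care sought | No | No | Ever |

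The care-seeking item is the only one in the table that names no condition. It is also the first item on the last page of the four-page form, so the two items before it are on the previous page.

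**Direction.** Take the intended quantity to be the share of surgeons who sought care for musculoskeletal symptoms. A surgeon who did so ticks a provider under either reading. A surgeon who did not, but saw a physician for something else, ticks a provider only under the literal reading. The ambiguity can therefore add to the count but not subtract from it.

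**Size per respondent.** The Sample size section gives 9 + 8 + 9 = 26. If all 26 answer and form the denominator, k respondents counted only because of unrelated care add k/26:

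- k = 0: 0 points
- k = 1: 1/26 = 3.8 percentage points
- k = 2: 2/26 = 7.7 percentage points
- k = 3: 3/26 = 11.5 percentage points

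The values of k are illustrative. The protocol gives neither a rate of unrelated care nor a rate of literal reading, so k cannot be estimated from it.

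**Would restricting to symptomatic surgeons remove the problem?** Only in part. Limiting the table to those who answered Yes to the opening item removes unrelated care among surgeons without symptoms. A surgeon with symptoms who saw a physician only for another illness would still be counted.

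**Time off against the objective.** The aim and the analysis line both refer to musculoskeletal symptoms without limiting them to work. Time off for any musculoskeletal injury is therefore inside the objective as written. The mismatch is with the prevalence item: a surgeon may truthfully answer No to work-related symptoms and Yes to time off, for example after a sports injury.

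**The case against.** The best reply is that nobody reads an item in isolation. This one sits in an ergonomics survey, under Ergonomic Questions, right after two items on musculoskeletal symptoms or injury. The next item asks about stretching or exercise for trouble areas. No treatment, the first option, makes sense only in relation to a problem already raised, and most of the listed providers are ones seen for musculoskeletal complaints. This stands, and it limits the finding: many respondents will probably infer the intended meaning. It does not remove the finding, because those who infer and those who read literally would be pooled with no means of separating them.

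A second reply is that the electronic form may skip the item for surgeons without symptoms, and a printout need not show this. That is possible. As shown in the working, it would narrow the problem but not close it.

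A third reply is that the protocol never names this item as an impact measure. That is correct, so the finding is about a risk to whatever percentage is reported from it.

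A reader might also infer three stronger things that the document does not support:

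- *That nearly every respondent would tick Physician, or that the burden is known to be overstated.* The context argues against the first, and no rate in the protocol establishes the second.
- *That counting injuries outside work breaks the first objective.* The objective carries no such limit.
- *That the stop-surgery item adds to the over-count because the form does not say which type of surgery is meant.* That item is expressly tied to musculoskeletal symptoms. Its vagueness about surgery type does not bring in unrelated care or injury.

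**Conclusion.** The point holds as a minor one. The care-seeking stem lacks the musculoskeletal reference that the items just before it carry, so the percentage drawn from it may be too high. The possible error is upward only, about 3.8 percentage points per respondent so counted if all 26 answer. Its total is unknown and could be zero. This rests on two assumptions: that the item will be reported as an impact measure, and that at least one respondent reads it literally.

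The time-off item is a secondary matter of consistency between two items on the same form. It does not depart from the stated objective.

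Only the descriptive first objective is touched. The before-to-after discomfort score, the linear mixed model and the Bonferroni adjustment do not use these items.

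**What to change.** Begin the care-seeking stem with the words *Because of work-related musculoskeletal symptoms* and leave the rest of the question and its options as they are. Adding *work-related* goes a step beyond naming the condition; it is suggested because it matches the prevalence item.

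Align the time-off item in the same way, for example by adding *work-related* before the reference to pain or injury, so that prevalence and impact describe the same condition. If the investigators do want time off for any musculoskeletal cause, they should say so and label that percentage accordingly.

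The cost is two wording edits to a form completed once, with no added items. The edits must be made before the form is sent out, since answers already collected could not be reclassified without going back to the respondents.

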## Pre-surgery questionnaire

*Confidential*

*Ergonomic survey*  
Page 1 of 1

### Pre-surgery questionnaire

Record ID \_\_\_\_\_

Today's date \_\_\_\_\_

#### Body part discomfort scores

- 1 Not uncomfortable
- 2 Barely uncomfortable
- 3 Quite uncomfortable
- 4 Very uncomfortable
- 5 Extremely uncomfortable

|                 | 1                     | 2                     | 3                     | 4                     | 5                     |
|-----------------|-----------------------|-----------------------|-----------------------|-----------------------|-----------------------|
| Neck            |  |
| Shoulder, right |  |
| Shoulder, left  |  |
| Hand, right     |  |
| Hand, left      |  |
| Lower back      |  |
| Upper back      |  |
| Knee, right     |  |
| Knee, left      |  |
| Foot, right     |  |
| Foot, left      |  |

## Post-surgery Control

Confidential

Ergonomic survey  
Page 1 of 2

## Post-surgery control

Record ID

Today's date

What case have you performed today?

[figure not shown]
- Thyroid
- Parathyroid
- Open neck
- Facial trauma
- Neck trauma
- Other

Other (please specify)

[figure not shown]
How long was the case? (in hours)

### GOAL and Surg-TLX subscales

[figure not shown]
Degree of difficulty- This procedure was:

[figure not shown]
#### Task Complexity: How complex was the procedure?

[figure not shown]
Distraction: How distracting was the operating environment?

**Mental Demand:** How mentally demanding was the procedure?

Physical demand: How physically demanding was the procedure?

Confidential

Page 2 of 2

**Body part discomfort scores:**

- 1 Not uncomfortable**
- 2 Barely uncomfortable**
- 3 Quite uncomfortable**
- 4 Very uncomfortable**
- 5 Extremely uncomfortable**

|                 | 1                     | 2                     | 3                     | 4                     | 5                     |
|-----------------|-----------------------|-----------------------|-----------------------|-----------------------|-----------------------|
| Neck            |  |
| Shoulder, right |  |
| Shoulder, left  |  |
| Hand, right     |  |
| Hand, left      |  |
| Lower back      |  |
| Upper back      |  |
| Knee, right     |  |
| Knee, left      |  |
| Foot, right     |  |
| Foot, left      |  |

What was your primary position during the surgery?

- Standing
- Seated
- Standing and Seated

What surgical equipments have you used during the case? (select all that applies)

- Headlight
- Robot
- Laparoscopic equipment
- Loupes
- Microscope
- Other

Other (please specify)

## Post-surgery Intervention

Confidential

Ergonomic survey  
Page 1 of 3

### Post-surgery intervention

Record ID

Today's date

What case have you performed today?

[figure not shown]
- Thyroid
- Parathyroid
- Open neck
- Facial trauma
- Neck trauma
- Other

Other (please specify)

How long was the case? (in hours)

#### GOAL and Surg-TLX subscales

[figure not shown]
Degree of difficulty- This procedure was:

[figure not shown]
Task Complexity: How complex was the procedure?

[figure not shown]
Distraction: How distracting was the operating environment?

Mental Demand: How mentally demanding was the procedure?

Physical demand: How physically demanding was the procedure?

Confidential

Page 2 of 3

**Body part discomfort scores:****1 Not uncomfortable****2 Barely uncomfortable****3 Quite uncomfortable****4 Very uncomfortable****5 Extremely uncomfortable**

|                 | 1                     | 2                     | 3                     | 4                     | 5                     |
|-----------------|-----------------------|-----------------------|-----------------------|-----------------------|-----------------------|
| Neck            |  |
| Shoulder, right |  |
| Shoulder, left  |  |
| Hand, right     |  |
| Hand, left      |  |
| Lower back      |  |
| Upper back      |  |
| Knee, right     |  |
| Knee, left      |  |
| Foot, right     |  |
| Foot, left      |  |

What was your primary position during the surgery?

Standing  
 Seated  
 Standing and Seated

What surgical equipments have you used during the case? (select all that applies)

Headlight  
 Robot  
 Laparoscopic equipment  
 Loupes  
 Microscope  
 Other

Other (please specify)

How often have you performed micro-break stretches?

Every 20 minutes  
 Every 30 minutes  
 Every 45 minutes  
 Every hour  
 Every 1.5 hours  
 Every 2 hours  
 Random time

How many micro-break stretches have you performed during the surgery?

Confidential

Page 3 of 3

| What is the impact of microbreak stretches have on... | Diminished            | Did not change        | Improved              |
|---|-----------------------|-----------------------|-----------------------|
| Physical performance                                  |  |  |  |
| Discomfort and pain                                   |  |  |  |
| Fatigue   |  |  |  |
| Mental focus  |  |  |  |

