**1= No distraction or no impact****10= Most distraction or most impact**

|   | 1                     | 2                     | 3                     | 4                     | 5                     | 6                     | 7                     | 8                     | 9                     | 10                    |
|---|-----------------------|-----------------------|-----------------------|-----------------------|-----------------------|-----------------------|-----------------------|-----------------------|-----------------------|-----------------------|
| To what degree, if any, did the exercise distract you from performing or assisting in the surgical procedure? |  |
| To what degree, if any, would you say that the exercises impacted the flow of the surgery?                    |  |

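### On the intervention-day impact grid, a tick under 'Diminished' for pain or fatigue can mean benefit or harm, and the form gives no key

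*Protocol*

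**What the plan says.** The Protocol's outcome measures (Methods, Study design) include "Secondary outcome= impact of OSMB on physical performance, discomfort/pain, fatigue, and mental focus". The instrument for this is the grid on page 3 of the Post-surgery Intervention questionnaire. Its stem is "What is the impact of microbreak stretches have on", followed by four rows: "Physical performance", "Discomfort and pain", fatigue and mental focus. All four share the same three columns: *Diminished*, *Did not change*, *Improved*. No instruction or key states which direction is favourable.

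The other ratings printed nearby do explain themselves. The grid directly below fixes both of its ends, "1= No distraction or no impact" and "10= Most distraction or most impact". The body part discomfort scores label every point, up to "Extremely uncomfortable".

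**The concern.** Two of the four rows name states of which more is better (performance, focus). The other two name symptoms of which less is better (discomfort and pain, fatigue). *Improved* judges a result, whereas *Diminished* in ordinary use describes a quantity. On the symptom rows the two words are therefore not clear opposites. A surgeon whose pain eased could tick *Improved* because the result is better, or *Diminished* because there is less pain. The same benefit can land at either end of the scale.

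The fault is confined to one column on two rows, since *Did not change* and *Improved* are clear throughout. But it arises when the form is filled in. An analysis rule can assign a meaning to *Diminished*; it cannot recover the one intended. Respondents may differ from one another, and one respondent may differ between days. This is therefore a defect of the form, not a coding detail that a statistical analysis plan could settle.

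At stake is the size of the reported effect on half of the secondary outcome's components, and in some configurations its direction.

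**Working it through.** The protocol has no figure of its own to reproduce here. The check is a reading of the form, followed by simple bounds.

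**1. Meaning of *Diminished* by row**

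| Row | Possible meaning | Other rating in the protocol |
|---|---|---|
| Physical performance | worse only | not needed |
| Discomfort and pain | less pain (benefit) or worse result (harm) | 11-site discomfort scores, before and after surgery |
| Fatigue | less fatigue (benefit) or worse result (harm) | none |
| Mental focus | worse only | not needed |

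Fatigue appears only in the outcome list and in this row. The 11-site scores record discomfort but not what the respondent credits to the stretches, so they check the pain row only indirectly. The performance and focus rows do not settle the symptom rows either: focus can improve while fatigue rises.

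**2. Bounds on net benefit**

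Let I and D be the shares ticking *Improved* and *Diminished* on a symptom row. Take *Improved* as better, and let *Diminished* be any mixture of better and worse.

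- True better lies in [I, I + D] and true worse in [0, D].
- Net benefit (better minus worse) therefore lies in [I − D, I + D], a width of 2D.
- The sign is certain if I > D.
- Scoring *Diminished* as worse reports I − D, the lower end, and understates by 0 to 2D. Scoring it as less of the symptom reports I + D, the upper end.

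**3. Scale**

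The Sample size section gives N = 26, and the design gives "Intervention: 3 OSMB surgical days". Assuming full enrolment and one form per participant per day, there are 26 × 3 = 78 forms. One *Diminished* tick then leaves 2/78 = 2.6 percentage points undetermined. With half as many forms (39) it is 2/39 = 5.1 points; with twice as many (156) it is 2/156 = 1.3 points.

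**4. Illustrations out of 78 forms (assumed counts)**

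| *Improved* | *Diminished* | Lower end | Upper end |
|---|---|---|---|
| 39 | 8 | 31/78 = +39.7 | 47/78 = +60.3 |
| 39 | 16 | 23/78 = +29.5 | 55/78 = +70.5 |
| 39 | 23 | 16/78 = +20.5 | 62/78 = +79.5 |
| 23 | 31 | −8/78 = −10.3 | 54/78 = +69.2 |

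In the first three rows the sign is known but the size is not. In the last, even the sign is open.

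**5. The same point from assumed true values**

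Let b truly benefit, w truly get worse, and a fraction m of those who benefit tick *Diminished*. Scored as worse, the observed net is b(1 − 2m) − w, against a true net of b − w. With b = 60% and w = 5%, neither from the protocol, the true net is +55 points. The observed net is +43 at m = 10%, +25 at m = 25% and −5 at m = 50%.

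**The case against.** The strongest reply is that context points to one reading. *Diminished* stands opposite *Improved*, with *Did not change* between them. The first row, physical performance, sets left as worse and right as better before the symptom rows are reached. Under the other reading, both outer columns would record benefit and none would record harm. This stands as an argument that *Diminished* meaning worse is the likelier reading. It does not exclude the other, and a minority of misreadings is enough to distort the result.

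Several further points also stand:

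- The counts above are illustrative, and the bounds treat every *Diminished* tick as uninformative. Net benefit is this review's summary, not one the protocol defines.
- Under the natural scoring the error is conservative: it understates benefit and does not create it.
- Scoring the column both ways gives usable bounds, and the exit questionnaire adds another indirect check.
- The grid below defines only its two ends, and bare numbers need a key more than verbal labels do. The comparison with other scales is supporting evidence only.

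Respondents in so small a group could be asked afterwards what they meant. That relies on recall across several operating days, and clear labels make it unnecessary.

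**Conclusion.** The concern holds. On two of the four rows of a named secondary outcome, one of the three response columns has two opposite meanings, and the form does not choose between them. Each tick in that column leaves 2.6 percentage points of net benefit undetermined at 78 forms, a count that assumes full enrolment and one form per participant-day. The most probable consequence is attenuation of unknown size, with the direction still known whenever *Improved* outnumbers *Diminished*. Fatigue is the row most exposed.

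The wording fault is certain; its practical effect is not, because the protocol gives no basis for predicting how many respondents will tick *Diminished*. The *Improved* and *Did not change* answers remain usable. The primary outcome, the before/after body part discomfort score, is not touched. This should be fixed because the remedy is so cheap, not because it threatens the trial's main result.

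**What to change.** Relabel the three columns *Worse*, *No change*, *Better* for all four rows of the grid on page 3 of the Post-surgery Intervention questionnaire. These words carry the same direction for symptoms and for positive states, so no separate key is needed. The change adds no item, respondent time or analysis.

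The protocol does not show whether forms are already in use. If some have been completed, record which version each answer came from. Report the old *Diminished* answers on the pain and fatigue rows separately, with net benefit given as the range I − D to I + D.
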